9.5. ECG

A 12-lead ECG will be performed locally at the site, and obtained at Screening, and pre-dose and 1 hour post dose on Day 1 for all subjects.

A shift table of the investigators' assessment of ECG results at each visit compared with baseline values will be presented by treatment group using the following categories: normal; abnormal (not clinically significant); abnormal (clinically significant). The number and percentage of subjects in each cross-classification group of the shift table will be presented by dose group and overall. Subjects with a missing value at baseline or post baseline will not be included in the denominator for percentage calculation.

A by-subject listing will be provided, including each ECG parameter: ventricular heart rate (beats per minute [bpm]), PR interval [msec], RR interval [msec], QRS Duration [msec], QT interval [msec], QTcB interval [msec], QTcF interval [msec] and investigator's interpretation. Potentially clinically significant QTcF values will be flagged in the listing.

The number and percentage of participants with PCS and potentially clinically significant change (PCSC) values will be summarized by visit/timepoint and for any time post-baseline. Potentially clinically significant values will be identified for ECG parameters as outlined below.

Table 10.5.1: Potentially Clinically Significant Values for QT, QTcF, QTcB

This document is confidential.

ECG Parameter	Units	Criteria for PCS Values (Observed values)		Criteria for PCS values (Change from Baseline values)	
		High	Low	Increase	Decrease
QT, QTcF	msec	>450 but <=480 >480 but <=500 >500	NA	>=30 to 60 >60	NA

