dL	deciliter
DLT	Dose–Limiting Toxicity
ECG	Electrocardiogram
FDA	Food and Drug Administration
FEF ₂₅₋₇₅	Forced Expiratory Flow between 25 and 75% of the FVC
FEV ₁	Forced Expiratory Volume in 1 second
FVC	Forced Vital Capacity

This document is confidential.

Statistical Analysis Plan for Interventional Studies

Sponsor: Armata Pharmaceuticals, Inc.; Protocol No.: AP-PA02-101

Abbreviation	Description
GCP	Good Clinical Practice
GLI	Global Lung Function Initiative
ICH	International Conference on Harmonization
INR	International Normalized Ratio
kg	kilogram
L	liter
LABA	long-acting inhaled β -agonist
LLQ	lower limit of quantification
LPS	lipopolysaccharide
MAD	Multiple Ascending Dose
Max	Maximum
μ g	microgram
μ L	microliter
MedDRA	Medical Dictionary for Regulatory Activities
mEq	milliequivalent
mg	milligram
mL	milliliter
mmHg	millimeters of mercury
mmol	millimole
Min	Minimum
MOI	multiplicity of infection
N/A	Not Applicable
NA	Not Applicable
OR	Observational Research
PASS	Post Authorization Safety Study
PAES	Post Authorization Efficacy Study
Pa, P. aeruginosa	Pseudomonas aeruginosa
PFU	plaque-forming unit
PT	prothrombin time, preferred term
PTT	partial thromboplastin time
qs	quantity sufficient

This document is confidential.

Statistical Analysis Plan for Interventional Studies

Sponsor: Armata Pharmaceuticals, Inc.; Protocol No.: AP-PA02-101

Abbreviation	Description
QTc	corrected QT interval
QTcB	corrected QT interval using Bazett's formula
RR	respiratory rate
SABA	short-acting inhaled β -agonist
SAD	Single Ascending Dose
SAE	Serious Adverse Event
SAP	Statistical Analysis Plan
SMC	Safety Monitoring Committee
SD	Standard Deviation
SE	Standard Error
SI	Standard International System of Units
SOC	System Organ Class
SOP	Standard Operating Procedure
SUSAR	Suspected Unexpected Serious Adverse Reaction
ULN	upper limit of normal
TEAE	Treatment Emergent Adverse Event
TFL	Table, Figure and Figure
WHO	World Health Organization

This document is confidential.

2. Purpose

The purpose of this statistical analysis plan (SAP) is to ensure that the data listings, summary tables and figures which will be produced, and the statistical methodologies that will be used, are complete and appropriate to allow valid conclusions regarding the study objectives.

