9.2.1. Adverse Events of Interest

The AEs of interest include the following:

- Hypotension
- Acute Bronchospasm
- Hypoxia
- Tachycardia
- Acute Urticaria

These AEs of interest are commonly seen with inhaled products. If AEs of interest occur at a Grade 3 level or higher in two or more subjects in a cohort, then an additional 4 subjects (3 active, 1 placebo) may be added to the cohort. Any of the Grade ≥ 3 toxicities for the AEs of interest as well as any other respiratory AEs reported, will be evaluated and considered when making dose escalation decisions. If no additional subjects experience any Grade ≥ 3 AEs of Interest, dose escalation may proceed (if recommended by the SMC).

In addition, a dose-limiting toxicity (DLT) is defined as follows, determined by the Investigator as study drug related:

- Allergic reaction requiring urgent medical intervention
- Acute bronchospasm requiring urgent medical intervention
- Hypotension accompanied by other evidence of a systemic inflammatory reaction or sepsis
- Other acute AEs requiring urgent medical intervention

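### Table 10.5.1 applies one set of limits to both uncorrected QT and QTcF, so heart rate alone can create QT flags, and gives no criteria for the QTcB in its title

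*SAP*

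**What the plan says.** All of this is in SAP Section 9.5.

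- **Title.** It names three intervals: "Table 10.5.1: Potentially Clinically Significant Values for QT, QTcF, QTcB".
- **Row.** The only row is labelled for QT and QTcF. Its observed-value categories, in msec, are ">450 but <=480 >480 but <=500 >500". Its change-from-baseline categories are 30 to 60 and above 60 msec. One set of limits serves both intervals.
- **Use.** "The number and percentage of participants with PCS and potentially clinically significant change (PCSC) values will be summarized by visit/timepoint", and also for any time after baseline.
- **Listing.** It shows ventricular rate and RR and also "QT interval [msec], QTcB interval [msec], QTcF interval [msec] and investigator's interpretation". Only one interval is marked: "Potentially clinically significant QTcF values will be flagged in the listing".
- **Timing.** ECGs are "obtained at Screening, and pre-dose and 1 hour post dose on Day 1 for all subjects".

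The glossary in Section 1 defines QTcB as the "corrected QT interval using Bazett's formula".

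**The concern.** The section gives three answers to the question of which intervals are screened: three in the title, two in the row and one in the listing flag. A programmer cannot tell from this whether QTcB counts are wanted or, if so, against which limits.

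The second problem is the shared limits. QTcF is adjusted for heart rate and QT is not, so a given number of msec does not mean the same thing for the two. A slow rate lengthens QT and a fast rate shortens it with no change in repolarisation. The plan would then report the slow-rate case as potentially clinically significant.

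Changes in heart rate are foreseeable here. Tachycardia is among the adverse events of interest in Section 9.2.1, which says of that list: "These AEs of interest are commonly seen with inhaled products". A rise in rate moves uncorrected QT in the reassuring direction.

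The groups are also small. Cohorts 1 to 3 have 3 active subjects each (Sections 3.4.1 and 3.4.2), so one rate-driven flag reads as 1/3 = 33% of an active group.

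**Working it through.** The plan gives no figure to reproduce here, so the check is direct arithmetic.

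**Inputs.** The limits come from Table 10.5.1. QTcF is taken in its usual meaning, the Fridericia correction, because the glossary does not define it. QTcB is Bazett, as the glossary says. The heart rates and QTcF values are illustrative assumptions; the SAP gives no ECG data.

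**Formulas.** With RR = 60/HR in seconds:

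- QTcF = QT / RR^(1/3), so QT = QTcF × (60/HR)^(1/3)
- QTcB = QT / RR^(1/2), so QTcB = QTcF × (HR/60)^(1/6)

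**Results by heart rate (msec).**

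| HR (bpm) | QT if QTcF = 420 | QT if QTcF = 490 | QTcF equivalent to QT 450 | QTcB if QTcF = 430 |
|---|---|---|---|---|
| 45 | 462.3 | 539.3 | 408.9 | 409.9 |
| 50 | 446.3 | 520.7 | 423.5 | 417.1 |
| 60 | 420.0 | 490.0 | 450.0 | 430.0 |
| 75 | 389.9 | 454.9 | 484.7 | 446.3 |
| 80 | 381.6 | 445.2 | 495.3 | 451.1 |
| 100 | 354.2 | 413.3 | 533.5 | 468.2 |

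**1. Observed-value flags created by rate.** QTcF 420 at 45 bpm gives QT = 420 × (60/45)^(1/3) = 462.3, which is above 450. The crossing point for QTcF 420 is 60 × (420/450)^3 = 48.8 bpm; below that rate QT is flagged although QTcF is not.

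**2. Change flags created by rate.** QTcF is held at 420 throughout.

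- 75 to 60 bpm: 420.0 − 389.9 = +30.1, in the 30 to 60 category.
- 100 to 60 bpm: 420.0 − 354.2 = +65.8, in the above-60 category.

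In both cases the QTcF change is 0.

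**3. QT count at fast rates.**

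- QTcF 490 at 100 bpm gives QT 413.3, so there is no QT flag. QTcF 490 itself falls in the category above 480 and up to 500, so the subject is flagged.
- QTcF rising from 410 at 60 bpm to 450 at 70 bpm gives a QT change of 450 × (60/70)^(1/3) − 410 = +17.5, so there is no QT flag. The QTcF change is +40, so the subject is flagged.

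**4. Whether QTcB would add anything.** With QTcF 430, QTcB passes 450 above 60 × (450/430)^6 = 78.8 bpm. Including or leaving out QTcB would therefore change the counts.

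**5. If the same limits apply to QTcF only.** A subject with QTcF constant at 420 gets no flag at any heart rate.

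**The case against.** **A reader might infer that the table hides prolongation.** It does not. QTcF is in the same row with the same limits, and step 3 shows that each case missed under QT is caught under QTcF. Only the QT count is uninformative there.

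**A reader might infer that QT and QTcF are pooled into one count.** The SAP does not say so. A row naming two parameters with shared criteria reads most naturally as two tabulated parameters.

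**A reader might infer that table and listing contradict each other.** Flagging only QTcF in the listing is a narrower display, and QTcF results would match in both. What remains is a traceability nuisance: a tabulated QT flag has no mark in the source listing.

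**A reader might link the missing QTcB to the heart-rate effect.** They are separate points. The rate effect comes from the QT entry alone.

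**Mitigation in the plan.** The investigator's overall ECG reading is tabulated separately as shifts from baseline. Rate and RR are listed beside each QT, so a rate-driven flag can be recognised on inspection. Section 9.4 also has heart-rate criteria, but only above 120 or below 40 bpm and with none for change. The 45 bpm example and the fall from 75 to 60 bpm would pass unmarked there.

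**QTcB.** A page break falls between the title and the row, so a lost entry in the text as extracted cannot be fully excluded. The row reads as complete, and the shared-limits point stands either way.

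**Stakes.** The expansion and escalation criteria in Section 9.2.1 rest on adverse events, not QT. This objection stands and keeps the point minor.

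**Conclusion.** The point holds in a limited form. The plan tabulates uncorrected QT against the same limits as QTcF, so heart rate alone can generate counts labelled potentially clinically significant. On illustrative values this takes a rate below about 49 bpm at QTcF 420 msec, or a fall of 15 bpm (75 to 60) between pre-dose and 1 hour post dose. In Cohorts 1 to 3 a single such flag is one active subject in three. Separately, the title names QTcB, which is listed but has no criteria.

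The QTcF screen is intact, and no primary or secondary endpoint is touched. The sizes rest on assumed heart rates and QTcF values and on the Fridericia formula for QTcF; how often such flags would occur in this trial cannot be judged from the SAP. This is a minor correction to descriptive safety output.

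**What to change.** In Section 9.5:

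- Apply the tabulated observed-value and change thresholds to rate-corrected intervals only: QTcF, and QTcB in its own row if it is meant to be screened. If it is not, take QTcB out of the title.
- Keep uncorrected QT in the by-subject listing, without these thresholds.
- Make the table title, the row label and the listing flag name the same intervals.
- Add QTcF to the glossary with its formula, next to QTcB.

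The cost is an edit to one table, one sentence and one glossary line, plus the matching programming specification. No new data are needed, since all the intervals are already in the listing.

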9.6. Physical Examination

Complete physical examinations (urogenital exams not required) will be performed at Screening, Baseline and Visit 5 for subjects enrolled in the SAD cohorts. For MAD Cohorts, complete physical examinations will be performed at Screening, Baseline, and/or at the EOS Visit.

A by-subject listing will be provided, including body system and result by dose group and overall.

9.7. Spirometry

Spirometry assessments FEV₁, FVC, and FEF₂₅₋₇₅ will be collected to evaluate for provoked bronchospasm. Actual liter values will be recorded. Details regarding spirometry procedures and standards will be included in the Study Manual.

Observed values and mean changes from baseline will be presented for each spirometry parameter using descriptive statistics (i.e. n, mean, standard deviation, median, minimum, and maximum) by dose group and visit, using the Safety population. If multiple measurements are to be performed at each time point, the highest value will be used for analysis.

A by-subject listing will be provided, including each spirometry parameter, and will be sorted by subject and visit.

A by-subject line plot will be presented by spirometry parameter, study part and dose group. Each dose group will be on a new plot, with all subjects of the same dose group on the same plot. Any unscheduled results will also be part of this plot.

The number and percentage of participants with PCS values will be summarized by visit/timepoint and for any time post-baseline. Potentially clinically significant values will be identified for FEV₁ (forced expiratory volume) as outlined below.

Table 10.7: Potentially Clinically Significant Values for Forced Expiratory Volume Decrease

Parameter	Units	Criteria for PCS Values (Observed values)	
		High	Low
Forced Expiratory Volume	%	NA	70 – 99 60 – <70 50 – <60 <50

This document is confidential.

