3.6. Determination of Sample Size

The sample size is not based on power calculations; it is chosen based on clinical experience and considered to be adequate to fulfill the objectives of the study.

Eight subjects were planned to be enrolled in the SAD portion of the study, with 4 subjects per cohort (3 AP-PA02 and 1 placebo).

Approximately 24 subjects will be enrolled in the MAD portion of the study, with 4 subjects in Cohort 3 (3 AP-PA02 and 1 placebo) and 20 subjects in Cohort 4 (15 AP-PA02 and 5 placebo). The exact number of subjects enrolled is dependent on whether any dose level is to be expanded due to the occurrence of dose-limiting toxicities (DLT).

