6.4. Visit Windows

There will be no derivation for visit windows in terms of summary assessments. Nominal visits will be used for by-visit tables.

For data with repeated observations at a given visit, for example, laboratory assessments, the earliest of the available non-missing values at a visit should be used in summary tables. Other observations will be considered as unscheduled visits. For the purpose of tabulations, the unscheduled post-baseline values generally will be excluded from summary tables, but will be included in the listing. Unscheduled visits will be considered for analyses of worst CTCAE laboratory grades.

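### The highest-value rule in SAP Section 9.7 does not suit FEF25-75: where several blows are recorded, it favours the less complete ones

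*SAP*

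**What the plan says.** Section 9.7 of the SAP treats FEV1, FVC and FEF25-75 together. It says that they "will be collected to evaluate for provoked bronchospasm", so their purpose is safety. The planned output is the same for all three: "Observed values and mean changes from baseline will be presented for each spirometry parameter using descriptive statistics", with listings and by-subject line plots.

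One rule covers repeated blows: "If multiple measurements are to be performed at each time point, the highest value will be used for analysis". No parameter is excepted, and FEF25-75 is not tied to the blow that supplies FEV1 or FVC.

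The glossary in Section 1 defines FEF25-75 as "Forced Expiratory Flow between 25 and 75% of the FVC". The SAP states no criterion for an acceptable blow. It defers that kind of detail elsewhere: "Details regarding spirometry procedures and standards will be included in the Study Manual". The manual is not among the documents at hand.

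**The concern.** Taking the largest FEV1 and the largest FVC rewards full effort, because a blow that stops early cannot raise either. FEF25-75 behaves differently. Its measuring window is set by the FVC of the same blow. A blow cut short has a smaller FVC, so the 25-75% window moves towards the start of expiration, where flow is faster. Applied to this parameter, the highest-value rule tends to pick the less complete blow.

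What is at stake is the reading of a descriptive safety parameter in small groups: three active subjects in each of Cohorts 1 to 3 and 15 in Cohort 4. If blows were cut short more often after nebulisation, for example by cough, the rule could partly hide a post-dose fall in FEF25-75.

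**Working it through.** The SAP gives no figure on this point, so there is nothing to reproduce. The direction follows from the glossary definition and from flow falling as the lung empties. The size needs assumptions, which are marked as such.

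**Inputs.** From the SAP: the selection rule and the parameters it covers (Section 9.7), and the definition of FEF25-75 (Section 1). Assumed: the emptying curve, three blows per time point, the completeness *f* of each blow (fraction of the full FVC reached), and the effort noise.

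**Step 1: one truncated blow against one complete blow.** With exponential emptying, V(t) = V0·(1 − exp(−t/τ)), a blow that ends at fraction *f* gives

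FEF25-75(f) = 0.5·f·V0 / (τ·ln[(1 − 0.25f)/(1 − 0.75f)]).

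For a complete blow this is 0.5·V0/(τ·ln 3). The ratio to the complete blow is therefore f·ln 3 / ln[(1 − 0.25f)/(1 − 0.75f)].

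- f = 0.95: 0.95 × 1.0986 / ln(0.7625/0.2875) = 1.0437/0.9754 = 1.070, a rise of 7.0%.
- f = 0.90: 0.9888 / ln(0.775/0.325) = 0.9888/0.8690 = 1.138, a rise of 13.8%.
- f = 0.85: 0.9338 / ln(0.7875/0.3625) = 0.9338/0.7758 = 1.204, a rise of 20.4%.
- f = 0.80: 0.8789 / ln 2 = 0.8789/0.6931 = 1.268, a rise of 26.8%.

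As a sensitivity check, a two-compartment (obstructive) curve was used: 60% of volume with time constant 0.4 and 40% with time constant 2.0. The rises are then 13.4%, 27.0%, 40.3% and 53.3%. The direction is the same and the size is larger.

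**Step 2: the rule itself.** The relevant error is the highest FEF25-75 of the session minus the value from the fullest blow. In 200,000 simulated time points, each had three blows with *f* uniform on the stated range, exponential emptying, and multiplicative effort noise with a CV of 0, 3% or 5%. The fullest blow was the one with the largest *f* (largest FVC).

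| Completeness of blows | Excess over fullest blow, noise 0 / 3% / 5% | Highest value comes from the shortest blow, noise 0 / 3% / 5% |
|---|---|---|
| 95-100% | 3.4% / 4.8% / 6.4% | 100% / 56% / 48% |
| 90-100% | 6.7% / 7.6% / 8.8% | 100% / 69% / 59% |
| 85-100% | 9.7% / 10.4% / 11.5% | 100% / 77% / 66% |
| 80-100% | 12.5% / 13.1% / 14.0% | 100% / 81% / 71% |

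By chance the shortest blow would supply the highest value in 33% of time points. With noise, part of the excess is the usual gain from taking the maximum of noisy values.

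Hand check of the last row without noise: among three uniform draws on 0.80-1, the expected shortest is 0.85 and the expected fullest is 0.95. From Step 1, 1.204/1.070 = 1.125, or 12.5%.

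**Step 3: change from baseline** (noise CV 3%, no true change).

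| Completeness at baseline → after dosing | Highest-value rule | Fullest blow |
|---|---|---|
| 90-100% → 90-100% | 0.0% | 0.0% |
| 95-100% → 85-100% | +8.9% | +3.4% |
| 85-100% → 95-100% | −8.1% | −3.3% |

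**The case against.** The strongest reply is that the problem may never arise. The rule in Section 9.7 is conditional on multiple measurements, and nothing in the SAP shows that several blows per time point reach the database. Blow quality is left to the Study Manual, and if that manual rejects incomplete blows before entry, most of the effect disappears. Both points stand and make the finding conditional. They do not change the fact that the SAP rule, as worded, points the wrong way for this parameter.

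Little also depends on FEF25-75. The exploratory endpoints in Sections 4.3.1 and 4.3.2 name FEV1 only, as do Section 9.7.1 and the table of potentially clinically significant values. Acute bronchospasm is captured directly as an adverse event of interest and within the definition of dose-limiting toxicity (Section 9.2.1), neither of which rests on FEF25-75. Section 6.1 adds that the study was closed early and that some outputs may not be produced. This stands and keeps the point minor.

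A reader might infer four stronger things that the documents do not support:

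- That FEF25-75 results are biased upwards throughout. The upward error is in observed values. In change from baseline it cancels when completeness is alike, and can otherwise have either sign.
- That the error is 7%, 14% or 27%. Those figures compare one truncated blow with one complete blow. The rule's own error is the smaller one in Step 2.
- That bronchospasm will be masked. This needs less complete blows after dosing than before, and the SAP gives no evidence of that. If every post-dose blow is short, no selection rule fully repairs it: the fullest-blow rule still shows +3.4%.
- That Section 6.4, under which "the earliest of the available non-missing values at a visit should be used in summary tables", contradicts Section 9.7. Section 6.4 is a general default for repeats at a visit, with laboratory data as its example. Section 9.7 is specific to spirometry within a time point, and the specific rule ordinarily governs.

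**Conclusion.** The point holds in conditional form and is minor. If several blows per time point are in the database, the stated rule favours less complete blows for FEF25-75 and overstates the observed values. Against the fullest blow the excess is about 3-6% at 95-100% completeness and about 12-14% at 80-100%.

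Only the direction comes from the SAP's definition. The sizes rest on the exponential curve, three blows, uniform completeness and 0-5% noise, all assumed. A more obstructive curve gives larger single-blow effects. The SAP states that "The sample size is not based on power calculations", and nothing here depends on power or on an assumed treatment effect. The FEV1 endpoint and the FEV1 safety thresholds are not touched.

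**What to change.** In Section 9.7, keep the highest value for FEV1 and for FVC. For FEF25-75, state that the value comes from one acceptable blow per time point, chosen on completeness, for example the blow with the largest sum of FEV1 and FVC. Select it in the same way at baseline and after dosing. The simulation used the largest FVC as the criterion; the largest sum is a close alternative that was not itself simulated.

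The cost is one sentence and one derivation if blow-level data are in the database. If only one value per parameter is recorded, no change is needed. No change to Section 6.4 is needed.

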3.5. Subject Selection

Subjects with cystic fibrosis and chronic pulmonary *Pa* infection who meet all inclusion and exclusion criteria will be eligible for participation in this study. The full list of inclusion and exclusion criteria is provided in Section 6.1.1 and 6.1.2 of the protocol.

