9.7.1. Change in FEV₁ from Baseline through End of Study

Forced Expiratory Volume in 1 second (FEV₁) (L) change from baseline and % Predicted FEV₁ change from baseline will be summarized by visit using summary statistics for continuous variables.

Percent predicted FEV₁ (%) will be calculated by implementing the Global Lungs Initiative 2012 regression equations. The predicted value of FEV₁ is a function of sex, age, height and ethnicity and is of this form:

$$M = \exp(a_0 + a_1 \cdot \ln(\text{Height}) + a_2 \cdot \ln(\text{Age}) + a_3 \cdot \text{black} + a_4 \cdot \text{NEAsia} + a_5 \cdot \text{SEAsia} + a_6 \cdot \text{Other} + \text{Mspline})$$

M = predicted value

Exp = exponential function

ln() = natural log transformation

black = 1 if a subject is African American, otherwise = 0

NEAsia = 1 if a subject is from North East Asia, otherwise = 0

SEAsia = 1 if a subject is from South East Asia, otherwise = 0

Other = 1 if subject is 'other ethnic group' or mixed ethnicity, otherwise = 0

coefficients a₀... a₆ depend on the measurement and gender

Mspline = age-varying coefficients

For 3-95 year-olds, Mspline is derived using linear interpolation with the assistance of a lookup table created by Qanjer, et. al. The lookup table contains values of known Mspline by age, and is used to calculate the unknown Mspline of the subjects age and sex. The coefficients used for predicted FEV₁ and a description of linear interpolation are provided in [Appendix 15.3](#).

Finally, % predicted = (measured/M) * 100.

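### Table 10.7 counts every FEV₁ value up to 99% as potentially clinically significant, does not define the percentage and has no change-from-baseline criterion, so its subject count cannot identify provoked falls

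*SAP*

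**What the plan says.** SAP section 9.7 states the purpose of spirometry: FEV₁, FVC and FEF₂₅₋₇₅ "will be collected to evaluate for provoked bronchospasm". For PCS values it plans this output: "The number and percentage of participants with PCS values will be summarized by visit/timepoint and for any time post-baseline".

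Table 10.7 sets the FEV₁ criteria. Its title is "Potentially Clinically Significant Values for Forced Expiratory Volume Decrease", its column head begins "Criteria for PCS Values (Observed values", its unit is a bare percent sign, and its Low column lists "70 – 99 60 – <70 50 – <60 <50". The High column is not applicable, and there is no column for change from baseline.

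The only FEV₁ percentage that the SAP defines is in section 9.7.1: "predicted = (measured/M) * 100", where M is the predicted value. Section 9.7 does not refer Table 10.7 to that definition.

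The other FEV₁ outputs are descriptive: "Observed values and mean changes from baseline will be presented for each spirometry parameter using descriptive statistics". By-subject listings and line plots are also planned.

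**The concern.** A PCS count is useful if few unaffected subjects meet the criterion and most affected subjects do. Here the criterion covers everything up to 99%, with one 29-point band above two 10-point bands and an open lowest band. Ordinary variation or existing lung disease can put a subject in the count without any reaction to the inhaled product.

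The undefined percentage adds to this. As a percentage of baseline, the bands describe falls. As a percentage of predicted, they describe levels, and a level says nothing about what the dose did. The title points to the first reading and the column head to the second.

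Safety and tolerability are the primary objectives, and the planned active groups are small (3, 3, 3 and 15 subjects, section 3.6). Table 10.7 is the only output in section 9.7 that counts subjects. If the count is near its ceiling in both placebo and AP-PA02, it cannot show whether one or two subjects reacted.

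**Working it through.** The SAP gives no figure to reproduce. The check applies the printed bands under each meaning of the percentage, with no drug effect.

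**From the SAP:** the four bands; the any-time post-baseline count; subjects described as "Subjects with cystic fibrosis and chronic pulmonary" *Pa* infection (section 3.5).

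**Assumed, because the SAP gives none:** within-subject CV of the analysed FEV₁ value 3% to 8%; 4 to 10 post-baseline readings; mean percent predicted 50 to 90 with SD 15 to 20, normally distributed.

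**Reading A, percent of baseline.** Band position by fall:
- A 1% fall gives 100 − 1 = 99, in the first band.
- A 30% fall gives 100 − 30 = 70, in the same band.
- A 30.1% fall gives 69.9, in the next band.

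Single reading: with CV 5% in both baseline and follow-up, the ratio has SD of about √2 × 5 = 7.07 points around 100. P(≤ 99) ≈ Φ(−1/7.07) = Φ(−0.141) ≈ 0.44.

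Any reading: simulation of 400,000 subjects. Baseline and each follow-up value were drawn as 1 + CV × N(0,1), divided by baseline, and the minimum taken over k readings.

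| CV | k | ever ≤ 99 | ever < 90 | ever < 80 |
|---|---|---|---|---|
| 3% | 4 | 71% | 2% | about 0% |
| 5% | 6 | 82% | 25% | 0.5% |
| 8% | 6 | 83% | 50% | 12% |
| 8% | 10 | 89% | 60% | 17% |

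The first band therefore mixes variation that most subjects show with falls that, at CV 5%, noise rarely produces. At CV 8% the separation is weaker, but the any-time count is still near its ceiling.

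**Reading B, percent predicted.** Share of readings flagged = Φ((99 − mean)/SD):

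| Mean | SD 15 | SD 20 |
|---|---|---|
| 50 | 99.9% | 99.3% |
| 60 | 99.5% | 97.4% |
| 70 | 97.3% | 92.6% |
| 80 | 89.7% | 82.9% |
| 90 | 72.6% | 67.4% |

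These are shares of readings. The share of subjects flagged at any time is at least as high. A stable subject at 65 is PCS at every visit.

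The largest relative fall that stays in the first band is (start − 70)/start:
- From 99: 29/99 = 29.3%.
- From 90: 20/90 = 22.2%.
- From 80: 10/80 = 12.5%.

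From 45, every fall stays in the lowest band.

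**Would splitting the top band be enough?** On reading A it would help: the table above separates falls below 80 from smaller ones. On reading B it would not. If only values below 90 were counted, the flagged share is Φ((90 − mean)/SD). That is 99.6% at mean 50, SD 15, and 84.1% at mean 70, SD 20. The missing element is a comparison with the subject's own baseline.

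**Comparison within the SAP.** Table 10.4.1 (vital signs) and Table 10.5.1 (ECG) both carry change-from-baseline criteria. Table 10.7 does not.

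**The case against.** The strongest objection is that section 9.7 does not depend on this table. It also plans by-subject listings and line plots with all subjects of a dose group together, unscheduled results included. Its change summaries give minimum and maximum, so the largest fall at each visit is visible. With 3 to 15 active subjects per group, individual falls can be read from the plots. Acute bronchospasm is an adverse event of interest (section 9.2.1), such events are counted by subject (section 9.2), and the escalation text refers to those events and the safety committee, not to Table 10.7. All of this stands. A reader might infer that the plan hides provoked bronchospasm; the documents do not support that. The limit is that plots and listings give no count, and the adverse-event table depends on an event being reported.

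A reader might also conclude that a 1% dip and a 30% fall always share a band. That is exact only for percent of baseline. On percent predicted, the fall that stays in the band depends on the starting level.

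It can also be said that band widths and the PCS threshold are clinical judgements, and that nothing in the SAP requires equal steps. That stands too: the point here is not which cut-off is right. The gap between 99 and 100 is trivial and disappears if percentages are rounded to whole numbers.

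Finally, the percent-of-baseline figures assume a CV and a number of readings. Section 9.7 takes the highest of multiple measurements at a time point, which the simulation does not model separately; the assumed CV has to be read as that of the value analysed. Even at CV 3% with 4 readings, about 71% of subjects are flagged.

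**Conclusion.** The point holds as a defect of the PCS count. As printed, Table 10.7 flags every FEV₁ value up to 99%, leaves the percentage undefined, has a title and column head that point to different quantities, and lacks the change criterion that its two companion tables have.

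The conclusion does not depend on which reading is meant: the count is high without any drug effect on both. The exact percentages do depend on the assumed CV, number of readings, means and SDs, none of which the SAP states. On percent predicted the saturation is weakest if subjects have near-normal lung function (67% to 73% of readings at an assumed mean of 90) and strongest if their function is reduced.

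The consequence is confined to this display. The count cannot identify provoked falls, while the other outputs can still show individual cases. The change is worth making before unblinding, because a threshold chosen afterwards could be influenced by the data.

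**What to change.** 1. State in section 9.7 what the percentage in Table 10.7 refers to, and reconcile the title with the column head.
2. Add a change-from-baseline section to Table 10.7, as in Tables 10.4.1 and 10.5.1. It should count subjects by relative fall in FEV₁ from their own pre-dose or baseline value (state which), by time point and at any time after baseline. The steps should be fine enough to separate small variation from falls approaching 30%.
3. If percent-predicted bands are kept, present them as a descriptive level or as a shift from baseline, not as the PCS count.
4. Have the sponsor's medical monitor set, before unblinding, the fall at which PCS starts. That cut-off is a clinical decision and is not proposed here.

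The cost is a few more table rows and some programming. No new data are needed.
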